###### Progressive Disease (PD):

At least a 20% increase in the sum of the diameters of target lesions, taking as reference the smallest sum on study with at least a 5 mm absolute increase in the sum of all lesions. The appearance of one or more new lesions\* denotes disease progression.

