**10.1.6 Progression-Free Survival**

Progression-Free Survival (PFS) is defined as the duration of time from start of treatment to time to progression event, including objective disease progression, clinical deterioration attributed to disease, or death.

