**Moving to Phase II Component:** Our hypothesis is that SGI-110 treatment will sensitize colon cancer patients to retreatment with irinotecan. Accordingly, it will be important to see that the dose of SGI-110 that is at the MTD does have pharmacodynamics effects at the tumor level. Patient tumor biopsies post-treatment will be analyzed by LINE assay for demethylation to assess for at least 10% demethylation from baseline in the tumor biopsies. We aim to see this level of demethylation in at least 60% of post-treatment biopsies as previously described in phase O studies.

**Phase II primary objective:** Evaluate the progression free survival (PFS) in patients receiving combination SGI-110 plus Irinotecan compared to standard of care treatment with regorafenib or TAS-102. Events are defined as disease progression or death from any cause. All patients treated

CONFIDENTIAL

This document is confidential. Do not disclose or use except as authorized.

on protocol will be included in the determination of PFS, regardless of treatment modification or discontinuation.

Epigenetic therapy may take several cycles to exert its maximal benefit, and preclinical data has demonstrated initial tumor growth is possible prior to tumor shrinkage. Patients on treatment with SGI-110 and IRI will be allowed to remain on study if their tumor progresses on RECIST 1.1 criteria if they are 1) clinically stable, 2) their provider feels it would be in their best interest, and 3) the patient is informed of scan results and consents to remain on treatment. In this circumstance, they will be reimaged on schedule after 2 further cycles. If this subsequent imaging confirms progressive disease, the date of the progression even will be dated to the first (initial) scan date that progression was first documented.

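### PFS in 14.1: a confirm-then-date progression rule covers only SGI-110 + irinotecan patients who continue past progression, and an unconfirmed, missing or pending repeat scan has no stated handling

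*Combined protocol and SAP*

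**What the plan says.** Section 14.1, under the Phase II primary objective, first gives a general rule: "Events are defined as disease progression or death from any cause". All treated patients are included "regardless of treatment modification or discontinuation".

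The next paragraph of the same text concerns one arm: "Patients on treatment with SGI-110 and IRI will be allowed to remain on study if their tumor progresses on RECIST 1.1 criteria". The patient must be clinically stable, informed and willing, and the provider must agree. Then "they will be reimaged on schedule after 2 further cycles", which is 8 weeks with 28-day cycles. The dating rule follows: "If this subsequent imaging confirms progressive disease, the date of the progression even will be dated to the first (initial) scan date". The reason given is that "preclinical data has demonstrated initial tumor growth is possible prior to tumor shrinkage".

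Elsewhere:
- Section 10.1.6 counts PFS events as "including objective disease progression, clinical deterioration attributed to disease, or death", with no confirmation condition.
- Section 10.1.4.1 defines target-lesion progression as "At least a 20% increase in the sum of the diameters of target lesions" over the smallest sum on study, with a 5 mm minimum. It has no confirmation step. Only equivocal new lesions await follow-up, and that rule is not limited to one arm.
- In the regorafenib/TAS-102 arm (Arm B), progression ends treatment (5.6) and opens crossover (5.8).
- The analysis paragraphs of 14.1 give no event or censoring rule for a first progression whose repeat scan is negative, absent or outstanding.

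**The concern.** The conditional sentence stands in the primary-endpoint text and fixes the date of an event, so it is more than permission to keep treating. It settles the confirmed case, where the event goes back to the first scan and nothing is gained by continuing. The other three cases are left open: not confirmed, not done, and pending at a data cut.

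Arm B patients stop at progression and have no repeat scan, so any progression set aside would be set aside in Arm A alone. The trial is open-label and site investigators read the images (4.3, 5.1.3). At stake are the final one-sided log-rank test and the futility look, which compares 4-month PFS between arms. Two analysts could count the same Arm A patient differently and both cite the protocol.

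**Working it through.** **1. The two readings**

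| Arm A patient who continues | First progression counts | First progression set aside |
|---|---|---|
| Repeat scan confirms | event at first scan | event at first scan |
| Repeat scan does not confirm | event at first scan | later event or none |
| Repeat scan missing | event at first scan | not stated |
| Repeat scan pending at the look | event at first scan | not stated |

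The first column rests on the event definition in 14.1, on 10.1.6 and on 10.1.4.1. The second rests on the condition in the dating sentence and its growth-before-shrinkage rationale. Only the first column is available in Arm B.

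**2. The plan's own figures**

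- Table 1 in 14.1, no-effect row: 5.4% rejection among studies not stopped × (1 − 0.264) = 4.0% overall, as printed.
- Stated control, median 1.9 months, taken as exponential: 0.5^(4/1.9) = 0.232, which matches the stated 23% at 4 months.
- Printed piecewise hazards: cumulative hazard at week 12 is 6 × 0.0113 + 6 × 0.0558 = 0.4026. The median is 12 + (0.6931 − 0.4026)/0.3238 = 12.9 weeks, about 3.0 months. At 4 months (17.3 weeks) PFS is exp(−(0.4026 + 5.33 × 0.3238)) = 0.12. This curve matches neither the stated median nor the stated 23%, so the exponential control is the main case here.

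**3. Why 4-month PFS is exposed**

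Scans are 8-weekly. A first progression at week 8 has its repeat at week 16. If that scan does not confirm, progression can next be recorded at week 24, after the 17.3-week mark. A set-aside progression at week 8 or 16 therefore turns a 4-month failure into a 4-month success.

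**4. Illustration with HR = 1**

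From the plan: 64 and 32 patients, 104 weeks of accrual, cut-off at week 208, 8-weekly scans, log-rank rejecting at z > 1.645. Assumed: the share p of Arm A scan-detected progressions set aside, each moved 16 weeks later (or to an earlier death or deterioration), and the share of events not found by scan (0% or 30%). There were 20,000 trials per cell.

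| Control curve, non-scan events | p = 0 | p = 2% | p = 5% |
|---|---|---|---|
| Exponential, 0% | 5.4% | 7.0% | 9.7% |
| Exponential, 30% | 5.7% | 6.5% | 7.9% |
| Piecewise, 0% | 5.5% | 7.6% | 12.0% |
| Piecewise, 30% | 5.5% | 6.5% | 8.1% |

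A separate simulation of the same cells agreed within about half a percentage point.

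In patients, p = 2% is 64 × 0.02 = 1.3, or 0.9 with 30% non-scan events (64 × 0.7 × 0.02). For p = 5% the figures are 3.2 and 2.2. A 2% share arises, for example, if 25% continue and 8% of those are not confirmed; 5% arises from 25% × 20%. Arm A 4-month PFS rises with no true effect by 0.9–1.6 points at 2% and 2.2–4.0 points at 5%, against a planned gain of 46.5 − 23 = 23.5 points.

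**5. Futility look**

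This used a stand-in rule, the z-value of the Kaplan-Meier 4-month difference at 32 + 16 patients, with its cut-off set to give the printed 26.4% stopping rate at HR = 1. It is not the plan's Dirichlet-process algorithm. Stopping falls to 22.8–24.7% at p = 2% and 18.4–22.1% at p = 5%. On average 3.3–4.8 of the 32 Arm A patients had a first scan progression in the 8 weeks before the look, so their repeat scan could still be pending.

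**The case against.** The best reply is that the default already exists. The first scan meets RECIST 1.1 progression by the plan's own words, 10.1.6 and 10.1.4.1 attach no confirmation, and continuation is framed in 5.1.3, 5.6 and section 10 as a treatment permission. On this view the dating sentence is protective, because it stops continued treatment from delaying the event date. No sentence says that an unconfirmed progression is discarded.

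Much of this stands. A reader might infer that the plan discards unconfirmed progressions in Arm A, or that every Arm A progression needs confirmation. The documents support neither: the doubt is confined to patients who continue and are then not confirmed, not rescanned or pending. The reply still does not close the gap. If every first progression counted regardless, the first-scan date would apply without any condition, and the stated rationale points the other way.

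The objection on size also stands. No unconfirmed share is documented, and low shares are the more plausible. The 12% figure needs both no non-scan events and a piecewise curve that disagrees with the stated median and 4-month PFS. Less frequent futility stopping mainly costs resources, since Table 1 shows only 5.4% rejection even among continuing null studies.

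**Conclusion.** The point holds as an unstated, arm-specific event rule for the primary endpoint, and it should be fixed. The direction is clear: setting a first progression aside lengthens Arm A PFS with no counterpart in Arm B.

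The size is not known. Under the assumptions shown, one-sided rejection with no true effect moves from about 5.5% to about 6.5–7.5% at a 2% share. At a 5% share it is about 8–10% with the stated exponential control, and up to about 12% with the printed piecewise hazards.

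These figures do not show that the trial's type I error is inflated. If the first progression is counted, the effect is nil. The case for acting rests on the open rule in an open-label, site-read trial, not on the illustrated percentages.

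**What to change.** In 14.1 and 10.1.6, state the following: in both arms, for the primary analysis and the futility look, objective progression counts as a PFS event at the first scan that meets RECIST 1.1 progression, with the equivocal-new-lesion rule of 10.1.4.1 applied in both arms. This holds whether or not treatment continues, whatever a later scan shows, and whether or not that scan is still pending. The other PFS events stay as the protocol defines them.

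Report PFS with confirmed-progression dating as a labelled sensitivity analysis, and say there how a missing or pending repeat scan is handled.

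Separately, reconcile 10.1.6 with 14.1: the former lists clinical deterioration as a PFS event and the latter does not. The answer should be the same in both arms; this point does not settle which.

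The cost is wording only, and the permission to continue treatment is untouched. The drawback is that true pseudo-progression in Arm A counts as an event, which is slightly conservative for that arm. The sensitivity analysis would show by how much. Another event rule would also close the gap if it were stated in advance and applied alike in both arms, but confirmation in Arm B would need a repeat scan that the plan does not have.

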**Phase II secondary objectives:**

1. Evaluate and compare response rates between arms of the study as determined by RECIST criteria 1.1.
2. Evaluate and compare overall survival (OS) between arms of the study.
3. Assess for potential predictive markers of survival using baseline tissue.
4. To assess the pharmacokinetics of SGI-110 in metastatic colon cancer patients and correlate with changes in global methylation.

**Sample Size/Accrual Rate:** The median PFS of patients on the phase III CORRECT trial of Regorafenib in metastatic colorectal cancer reported by Grothey and Van Cutsem was 1.9 months. The median PFS of patients on the phase III RECURSE trial of TAS-102 in metastatic colorectal adenocarcinoma reported by Mayer was 2.0 months. The PFS curves of these two trials were superimposable and therefore hazard rates over four time intervals were estimated based on the published PFS curve (figure 3.) for Regorafenib from the CORRECT trial. Simple linear regressions were used to fit the natural logarithm of the Kaplan-Meier product limit estimate of the PFS function as a function of time in four intervals: from 1 to 6 weeks, 6 to 12, 12 to 18, and 18 to 56 weeks. These estimated hazard rates: 0.0113, 0.0558, 0.3238, and 0.0748 per person week were used in simulations to evaluate power for this study. We hypothesize that the SGI-110 combination treatment will improve the 4 month PFS from 23% to 46.5%. Patients will be randomized to the SGI-110 + irinotecan (Arm A) and the Regorafenib or TAS-102 arm (Arm B) in a 2:1 ratio. Using a one sided 5% type I error allowance, accrual of 48 patients per year for 2 years (Arm A and B target sample sizes of 64 and 32 respectively) with an additional 2 years of follow up, this study will provide sufficient events to have 83% power to detect an improvement of the median PFS from 1.9 months to 3.6 months, i.e. a hazard ratio of 0.526.

**Quality of Life Assessment:** Quality of life will be assessed with the Functional Assessment of Cancer Therapy (FACT-C) quality of life tool. An overall quality of life score for the domains: physical well-being, social/family well-being, emotional well-being, and functional well-being, as well as the colon cancer specific subscale score will be obtained at the start of the study (Cycle 1 Day 1), at the beginning of cycle three (Cycle 3 Day 1), every other cycle subsequently (i.e. Cycle 5 Day 1, Cycle 7 Day 1, etc), and at the off study visit for every patient. Scoring will follow guidelines provided by FACIT administration guidelines manual. The change in total score between pre-treatment and the start of cycle three will be compared between arms of the study with a t-test. Two subscale sums of the total score: the sum of physical and functional well-being,

CONFIDENTIAL

This document is confidential. Do not disclose or use except as authorized.

and the sum of social/family and emotional well-being, will be similarly analyzed. The change in the colon cancer specific domain will also be compared between arms of the study. We anticipate that we will have minimal missing data at the start of cycle 3 as this is the first time a patient could come off study for progression. At this time point, any missing data would be due to DLTs, SAE events, or voluntary withdrawal. In these cases, documentation of the reason for missing data and the QoL at the time of withdrawal will be obtained with the off study evaluation.

**Futility monitoring plan:** We will monitor the study for futility using a non-parametric Bayesian predictive probability approach. This monitoring plan is based on calculations of the posterior distribution of the survival distribution and simulations to determine the probability that the PFS at 4 months on the treatment arm will be greater than that on the control arm at the end of the study. When the trial is monitored, Gibbs sampling is used to generate samples from the posterior distribution of the survival distribution via Monte Carlo simulation, given the data and a Dirichlet process prior. Censored observations are treated as random quantities and PFS event times are simulated for each censored observation. This is repeated many times and ultimately converges to a realization of the parameters drawn from the posterior distribution. The algorithm is that reported in Kuo and Smith. If the probability that the treatment 4 month PFS is greater than the control PFS at 4 months is very low, less than 33.3%, the study will be stopped for futility.

The reference hazard rates were estimated based on the published PFS curve (figure 3.) for Regorafenib. Simple linear regressions were used to fit the natural logarithm of the Kaplan-Meier product limit estimate of the survival function as a function of time in four intervals: from 1 to 6 weeks, 6 to 12, 12 to 18, and 18 to 56 weeks. Survival times were then generated using a piecewise exponential distribution with these estimated hazard rates: 0.0113, 0.0558, 0.3238, and 0.0748 per person week. For simulation purposes, the effect of treatment was assumed to multiply these hazard rates by factors of 1.0 (no difference), 0.80, 0.60, 0.526, 0.50, 0.40 and 0.35. The randomization ratio for these simulated studies was 2:1 and a single interim analysis, evaluating 4 month PFS, was performed after 50% of the patients were enrolled, i.e. n=32 in Arm A (SGI-110) and n=16 in Arm B (Regorafenib or TAS-102). A one-sided 0.05 alpha level log-rank test was used for the final analysis. Plots of the reference curve (black) and six scenarios of treatment effects (red) are shown in figure 1. In scenario one, the reference and treatment hazard rates are equal. Table 1 gives operating characteristics of this monitoring plan for these scenarios. Column 4 in table 1 is the proportion of studies rejecting the null hypothesis out of the number of studies that did not stop for futility. Column 5 is the overall proportion of studies with a positive result.

Table 1. Operating characteristics of monitoring rule from 500 simulated studies with interim analysis on 4 month PFS and final analysis based on the log-rank test.

Scenario	Control hazard rate ( $\lambda$ ) multiplier	Stop for Futility %	Rejected at final analysis %*	Overall studies rejecting Ho %
1	1.00	26.4%	5.4%	4.0%
2	0.80	12.8%	22.0%	19.2%

CONFIDENTIAL

This document is confidential. Do not disclose or use except as authorized.

3	0.60	5.2%	68.8%	65.2%
4	0.526	2.0%	84.7%	83.0%
5	0.50	1.2%	89.1%	88.0%
6	0.40	0.6%	98.4%	97.8%
7	0.35	0.0%	99.8%	99.8%

\*Denominator is the number of simulations that do not stop early for futility.

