#### Phase II Component: Stage II

- To improve median progression-free survival from that reported with regorafenib and TAS-102 to 4 months for SGI-110+irinotecan in previously treated metastatic colon cancer patients who have progressed on irinotecan.

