### 10.1 Antitumor Effect– Solid Tumors

For the purposes of this study, participants should be re-evaluated for response every 8 weeks. In addition to a baseline scan, confirmatory scans should also be obtained not less than 4 weeks following initial documentation of objective response.

Response and progression will be evaluated in this study using the new international criteria proposed by the Response Evaluation Criteria in Solid Tumors (RECIST) 1.1 guideline. Changes in the diameter (unidimensional measurement) of the tumor lesions are used in the RECIST criteria.

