### 14.1 Study Design/Endpoints

This is a Phase I/II study of Irinotecan and SGI-110 in patients with locally advanced or metastatic colorectal cancer. The dose escalation portion of the study will be used to determine the preferred dose of SGI-110, 30mg/m^2, 45 mg/m^2 or 60 mg/m^2, in combination with Irinotecan. The second portion of this study will be an open-label randomized phase II study with one arm receiving combination SGI-110 plus Irinotecan at the recommended dose from phase 1 (determined to be SGI-110 45mg/m^2, Irinotecan 125mg/m^2, with mandatory growth factor support) and the other arm receiving Regorafenib or TAS-102 at the standard commercial dose. The primary objective of the study is based on a comparison of PFS in the SGI-110 arm to that in the Regorafenib or TAS-102 arm, the two approved standard of care drugs in this setting. The primary endpoint for the Phase II study will be progression free survival (PFS). The study will randomize patients to the SGI-110 versus Regorafenib or TAS-102 at a ratio of 2:1. The randomized Regorafenib or TAS-102 group will provide information about PFS with the standard of care drugs to verify assumptions made in the design of the study.

**Phase I primary objective:** To assess safety and tolerability of Irinotecan in combination with SGI-110 in patients with advanced colon cancer. Determine the maximum tolerated dose (MTD) of Irinotecan in combination with SGI-110 and recommend a dose for phase II study.

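### Section 14.1's printed control hazards imply a 3.0-month median and 12% 4-month PFS, not 1.9 months and 23%, and its stated design gives about 88–90% power, not 83%

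*Combined protocol and SAP*

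**What the plan says.** All of this is in Section 14.1 unless noted.

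- **Headline design (Sample Size/Accrual Rate).** 64 versus 32 patients, 48 per year for 2 years, 2 further years of follow-up, one-sided 5% type I error, HR 0.526: "this study will provide sufficient events to have 83% power to detect an improvement of the median PFS from 1.9 months to 3.6 months".
- **Hypothesis in the same paragraph.** "We hypothesize that the SGI-110 combination treatment will improve the 4 month PFS from 23% to 46.5" (percent). The 1.9 months is the median reported for regorafenib in the cited phase III trial; the TAS-102 trial is cited as 2.0 months.
- **Basis of the power.** "These estimated hazard rates: 0.0113, 0.0558, 0.3238, and 0.0748 per person week were used in simulations to evaluate power for this study". The intervals are 1–6, 6–12, 12–18 and 18–56 weeks.
- **Futility monitoring plan.** The same rates are repeated: "Survival times were then generated using a piecewise exponential distribution with these estimated hazard rates: 0.0113, 0.0558, 0.3238, and 0.0748 per person week". The test is also repeated: "A one-sided 0.05 alpha level log-rank test was used for the final analysis". Table 1 (500 simulated trials) gives, for HR 0.526, 2.0% stopped for futility, 84.7% rejecting among the rest and 83.0% overall.
- **Use of the control arm (Study Design/Endpoints).** It "will provide information about PFS with the standard of care drugs to verify assumptions made in the design of the study".
- **Section 1.2, Phase II.** The objective is "To improve median progression-free survival from that reported with regorafenib and TAS-102 to 4 months".

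**The concern.** Section 14.1 carries two control curves. One is in the hypothesis (median 1.9 months, 23% at 4 months). The other is the set of hazards said to drive the simulations. If they differ, the planned check of the design assumptions against the control arm has no clear meaning: an observed median near 2 months would confirm the text and refute the simulated curve. The size of the targeted benefit also depends on the curve. HR 0.526 is a median gain of 1.7 months on the text's figures (3.6 − 1.9), but 0.4 months on the printed hazards (3.41 − 2.97).

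Separately, nearly every patient should have had a PFS event after 2 + 2 years, and 96 events at this hazard ratio give more than 83% power at one-sided 0.05. If the simulation used a critical value, censoring pattern or analysis time other than those printed, that should be known before the final analysis.

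**Working it through.** **1. What does agree.** Table 1 is internally consistent: 84.7% × (1 − 0.020) = 83.0%. The hypothesis figures also agree with one another. 1.9/0.526 = 3.61 months, and for an exponential curve with median m, S(4) = 0.5^(4/m), so 0.5^(4/1.9) = 23.2% and 0.5^(4/3.6) = 46.3%. The text therefore matches a single-rate exponential.

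**2. The curve from the printed hazards.** S(t) = exp(−H(t)), with 4.348 weeks per month, so 1.9 months = 8.26 weeks and 4 months = 17.39 weeks.

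- H(12) = 6 × 0.0113 + 6 × 0.0558 = 0.4026, so S(12) = 66.9%.
- Control median = 12 + (0.6931 − 0.4026)/0.3238 = 12.90 weeks = 2.97 months.
- H(8.26) = 0.0678 + 2.26 × 0.0558 = 0.194, so S(1.9 months) = 82%.
- H(17.39) = 0.4026 + 5.39 × 0.3238 = 2.149, so S(4 months) = 11.7%.
- With HR 0.526, the median is reached at control H = 0.6931/0.526 = 1.318: 12 + (1.318 − 0.4026)/0.3238 = 14.83 weeks = 3.41 months. S(4 months) = exp(−0.526 × 2.149) = 32.3%.

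**3. Other readings.** Starting the first interval at week 1 gives 12.93 weeks and 11.8%. Taking 4 months as 16 weeks gives 18.3% and 40.9%. Over all 24 orders of the four rates, 4-month PFS is 7–12% or 43–45% (at 16 weeks, 7–18% or 44–50%), never near 23%. Swapping the second and third rates gives a 1.8-month median but 10% at 4 months. A transcription error is possible but would not by itself restore both figures.

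**4. Power by formula.** Schoenfeld, 2:1 allocation, 96 events: √(96 × 2/9) × |ln 0.526| = 4.619 × 0.6425 = 2.967. At one-sided 0.05, Φ(2.967 − 1.645) = 90.7%. At one-sided 0.025, Φ(2.967 − 1.960) = 84.3%. About 74 events would suffice for 83% at one-sided 0.05, 22 fewer than 96.

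**5. Power by simulation.** Settings: printed hazards, uniform accrual, 2 + 2 years, log-rank, no dropout, 4,000–6,000 trials per cell. About 96 events occur, and power at HR 0.526 without a futility stop is 90.1%. Subtracting Table 1's own 2.0% stop rate leaves at least 88.1%. The futility rule was then approximated by a normal posterior on Kaplan–Meier 4-month PFS at the 48th patient, stopping if P < 1/3. Overall rejection (%), all re-runs with the futility stop:

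| HR | Table 1 | As printed | One-sided 0.05, 8-week scan times | One-sided 0.025, continuous times |
|---|---|---|---|---|
| 1.00 | 4.0 | 5.7 | 4.7 | 3.0 |
| 0.80 | 19.2 | 26.9 | 22.0 | 18.6 |
| 0.60 | 65.2 | 73.1 | 66.7 | 63.0 |
| 0.526 | 83.0 | 88.2 | 85.2 | 81.8 |
| 0.50 | 88.0 | 91.8 | 89.7 | 86.8 |
| 0.40 | 97.8 | 99.0 | 98.7 | 98.4 |
| 0.35 | 99.8 | 99.7 | 99.3 | 99.5 |

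With 500 simulations the standard error at 83% is √(0.83 × 0.17/500) = 1.7 points. The re-run as printed is 2.6 to 4.4 standard errors above Table 1 at HR 0.80 to 0.50, so chance is a poor explanation.

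**6. Inputs that would close the gap.** Both right-hand columns fit Table 1 approximately. The 8-week schedule is in Section 10.1 ("For the purposes of this study, participants should be re-evaluated for response every 8 weeks"), but the simulation description does not mention it. At HR 0.526 and one-sided 0.05, an assumed 1% per week dropout gives 83.2%, and analysis at the end of accrual gives 83.5%.

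**7. Does the curve matter for power?** Hardly. At HR 0.526 with futility, power is 88.2% (printed), 89.5% (second and third rates swapped) and 88.7% (exponential, 1.9-month median). With 8-week scans it is 85.2%, 86.8% and 87.1%.

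**8. Target.** Section 1.2's 4 months against 1.9 is 1.9/4 = HR 0.475; Section 14.1 uses 0.526.

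**The case against.** The strongest reply has four parts.

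- **Month length.** The trial runs on 28-day cycles with 8-week scans, so 4 months may mean 16 weeks. The control gap then shrinks to about 5 points (18.3% against 23%). That is a fair qualification, but it does not restore 23% and does nothing for the median.
- **Unstated is not absent.** The simulation may have included dropout, scan times or an earlier analysis, and several such inputs land near 83%. This stands as to cause, which the documents cannot settle. It does not make 83% follow from the inputs that are printed.
- **The futility rule was approximated.** The prior mass is not given, and the approximation stops 32–33% of null trials against the printed 26.4%, so the with-futility figures should not be read to the decimal. The main result does not depend on it: power before the futility look is about 90%, and Table 1's own stop rate at HR 0.526 is only 2.0%.
- **Little follows from it.** Powering for 3.6 rather than 4 months is conservative, and the difference from Section 1.2 is mainly wording. The power error runs in the safe direction, and the plan attaches no decision rule to the check of the control arm. All true; this limits the weight of the point but does not make the figures consistent.

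**Conclusion.** The point holds. The hazards printed in two places contradict the stated planning figures: control median 3.0 against 1.9 months and 4-month PFS 12% (18% at 16 weeks) against 23%; at HR 0.526, 3.4 against 3.6 months and 32% (41%) against 46.5%. This part is hand arithmetic and needs no assumption beyond the month length.

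The stated 83% power is not reproduced by the stated design, which gives about 90% before and 88% after the futility stop. That assumes no dropout, continuous event times and analysis after 2 + 2 years, as printed. The scan-time runs round every event up to the next scan, so deaths between scans would raise those figures somewhat.

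The consequence is moderate. With the declared one-sided 0.05 test there is no power shortfall and no declared error rate is exceeded. What fails is the traceability of the sample-size justification and the meaning of the planned check against the control arm. It should be corrected, but it does not threaten the trial's validity.

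**What to change.** 1. Recheck the four fitted hazards, including their order and intervals, against the published regorafenib PFS curve. Start with the hazards, because the 1.9 and 2.0 months are cited trial results. Then make the hazards, medians and 4-month PFS agree, and say how many weeks 4 months means. Keep the piecewise form unless the check shows it is wrong.
2. Confirm from the simulation code the critical value, analysis time, censoring or dropout, scan-time handling and futility prior, and state them in Section 14.1.
3. Re-run Table 1, including the futility stop rates, with the corrected curve and the declared one-sided 0.05 test. Restate the power: expect about 88–90% with continuous times, about 85–87% if 8-week scans are modelled, and less with dropout.
4. Reconcile the 4-month objective in Section 1.2 with the 3.6 months in Section 14.1.

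Cost: a check of the fitted rates, one simulation re-run and protocol wording. No patients are added and alpha is unchanged.
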